8.4.1.2 Categories for Adverse Event Assessment

All AEs will be assessed and documented by the investigator according to the categories detailed below.

Seriousness

For each AE, the seriousness must be determined according to the criteria given in Section 8.4.1.5.

Confidential Page 49 of 71

Tc 99m tilmanocept Clinical Study Protocol Number: NAV3-30

Severity

The severity of an AE is classified according to the following categories, taking into account the possible range of the intensity of the event:

- Mild The AE is transient and easily tolerated by the subject.
- Moderate The AE causes the subject discomfort and interrupts the subject's usual activities
- Severe The AE causes considerable interference with the subject's usual activities and may be incapacitating or life-threatening.

Specific drug treatment

Any specific drug treatment will be documented.

Causal relationship to investigational product

The investigator will use the following definitions to assess the relationship of the AE to the use of investigational product:

Definitely related: Event can be fully explained by administration of the investigational

product.

Probably related: Event is most likely to be explained by administration of the

investigational product rather than the subject's clinical state or

other agents/therapies.

Possibly related: Event may be explained by administration of the investigational

product or by the subject's clinical state or other agents/therapies.

Probably not related: Event is most likely to be explained by the subject's clinical state or

other agents/therapies, rather than the investigational product.

Definitely not related: Event can be fully explained by the subject's clinical state or other

agents/therapies.

For causality assessments, events meeting the categories of definitely, probably, or possibly related will be considered to be related to investigational product.

Causal relationship to study procedure

The investigator will use the following definitions to assess the relationship of the AE to the study procedure:

Confidential Page 50 of 71

Clinical Study Protocol Number: NAV3-30 Date: 23 April 2018

Definitely related: Event can be fully explained by the study procedure.

Probably related: Event is most likely to be explained by the study rather than the

subject's clinical state or other agents/therapies.

Possibly related: Event may be explained by the study procedure or by the subject's

clinical state or other agents/therapies.

Probably not related: Event is most likely to be explained by the subject's clinical state or

other agents/therapies, rather than the study procedure.

Definitely not related: Event can be fully explained by the subject's clinical state or other

agents/therapies.

For causality assessments, events meeting the categories of definitely, probably, or possibly related will be considered to be related to study.

8.4.1.3 Assessments and Documentation of Adverse Events

Attention shall be paid to the occurrence of AEs for the duration of subject participation. Untoward medical events beginning on Visit 1 Screening (Days -45 to -1) through the completion of the Follow-up Telephone Call will be reported as AEs. Thus, subjects should be closely observed by the investigator both during and after the evaluation.

Any AE (observed, volunteered, or elicited) should be recorded in detail in the source documentation.

The following information is required:

- The date and time of onset of any AE.
- The duration (the entire duration of an event or symptom, calculated from date of onset to date of end, if not recorded directly).
- The seriousness of the AE will be assessed by the investigator. If the investigator deems that an AE qualifies as an SAE, a special form provided by the sponsor should be completed and the event must be immediately reported to the sponsor. A definition of SAEs is provided in Section 8.4.1.5.
- The maximum intensity (mild, moderate, or severe).
- Whether drug treatment was administered for the event, any specific drug treatment must be documented.
- The relationship of the AE to the investigational product and to study conduct (for definitions, see above).

The **outcome** of the AE (resolved, resolved with sequelae, not resolved, unknown, death).

AEs will be coded according to an internationally recognized dictionary (Medical Dictionary for Regulatory Activities [MedDRA]).

Confidential Page 51 of 71

Clinical Study Protocol Number: NAV3-30

8.4.1.4 Expected Adverse Events

Investigational Product-Related Risks

In all completed studies of Tc 99m tilmanocept, involving 575 subjects, only three events (breast pain and injection site pain reported by subjects with breast cancer and injection site irritation reported by a subject with head and neck squamous cell cancer) were deemed definitely related to the administration of Tc 99m tilmanocept by the investigator. The most commonly reported adverse reactions have been lack of effect (<0.067%), injection site pain (<0.02%) and rash (<0.02%). AEs from the radioactive dose are not expected, since the applied radiation doses are far below doses that can cause acute effects in human tissues.

Post-marketing surveillance shows that Tc 99m tilmanocept (Lymphoseek®) has been administered to more than 200,000 patients with not a single drug-related SAE. Routes of administration have included: subcutaneous, intradermal, and peritumoral. The intended route of administration in this study is IV.

Precautionary Measures

Special precautionary measures are not considered necessary for this study. In case of emergency, standard emergency procedures will be employed.

Unexpected Adverse Events

An unexpected AE is defined as an adverse reaction that in nature and severity is not consistent with the applicable product information (e.g., Investigator's Brochure). Any adverse experience that is not listed in the current Investigator's Brochure or which is, with regard to the specificity or severity, not consistent with the risk information shall be regarded as unexpected.

Examples would be (a) acute renal failure listed in the Investigator's Brochure with a subsequent new report of interstitial nephritis and (b) hepatitis with a first report of fulminant hepatitis. "Unexpected" as used in this definition refers to an adverse drug experience that has not been previously observed and included in the Investigator's Brochure, rather than from the perspective of such experience not being anticipated from the pharmacological properties of the investigational product.

8.4.1.5 Serious Adverse Events

Definition of Serious Adverse Events

Definition

The following SAE definition is based on ICH guidelines and the final rule issued by the FDA and effective 06 Apr 1998.

Confidential

Clinical Study Protocol Number: NAV3-30

An SAE is classified as any untoward medical occurrence that at any dose:

- results in death, or
- is life threatening, or
- requires inpatient hospitalization or prolongation of existing hospitalization, or
- results in persistent or significant disability/incapacity, or
- is a congenital anomaly/birth defect, or
- is an important medical event (see paragraphs below).

The term 'life threatening' in the definition refers to an event in which the subject was at risk of death at the time of the event; it does not refer to an event that hypothetically might have caused death if it were more severe.

Medical and scientific judgment should be exercised in deciding whether it is appropriate to report an AE as serious also in other situations, such as important medical events that may not be immediately life threatening or result in death or hospitalization but may jeopardize the subject or may require intervention to prevent one of the other outcomes listed in the definition above. These should also usually be considered serious. Examples of such events are intensive treatment in an emergency room or at home for allergic bronchospasm or blood dyscrasias or convulsions that do not result in subject hospitalization.

Actions and reporting obligations in case of serious adverse events

The investigator should take appropriate diagnostic and therapeutic measures to minimize the risk to the subject.

If any SAE occurs over the course of the study, investigators or other site personnel will inform Navidea Biopharmaceutical representatives within one day (i.e., within 24 hours) of becoming aware of the SAE. Written notification of the SAE will be emailed to Navidea Biopharmaceuticals Pharmacovigilance at [contact]. For fatal or life-threatening AEs where important or relevant information is missing, active follow-up is undertaken immediately.

Pregnancy will have the same time reporting obligations to the sponsor as SAEs. Upon notification, Navidea will provide a form for collection of pregnancy information.

All SAEs must also be recorded on the AE CRFs.

Notification of the IRB(s)

The sponsor and/or the investigator will notify the IRB(s) about all relevant events (e.g., SAEs and Suspected, Unexpected, Serious Adverse Reactions [SUSARs]) according to all applicable regulations.

Confidential Page 53 of 71

Notification of the authorities

The sponsor will process and report all relevant events (e.g., SAEs, SUSARs) to the authorities according to all applicable regulations.

Sponsor's notification of the investigators

The sponsor will inform all investigators about reported relevant events (e.g., SAEs, SUSARs) according to all applicable regulations.

8.4.2 Further Safety Assessments

8.4.2.1 Physical Exam

Complete physical examinations will be conducted according to the Schedule of Study Events (see Appendix 1). Height and body weight will be collected at Visit 1 (Screening).

Physical examinations will be performed for the following body systems:

- General Appearance
- Skin/dermatological
- Eyes, ears, nose, throat
- Head and neck (including thyroid)
- Lungs
- Heart
- Abdomen (liver, kidney, spleen, gastrointestinal)
- Musculoskeletal
- Nervous system

8.4.2.2 Vital Signs

Vital signs comprise the measurement of body temperature, heart rate, and respiration, systolic and diastolic blood pressure. All measurements will be taken after the subject has been in a resting position for at least 1 minute.

Vital signs will be measured at screening, within 15 minutes before each product administration, and 20 ± 5 minutes after each product administration.

Any clinically significant change from screening (worsening) that results in a change in subject management will be considered an AE and will be recorded on the AE page of the CRF.

8.4.2.3 Electrocardiogram

A standard 12-lead ECG will be obtained at screening and 20 ± 5 minutes following Tc 99m tilmanocept administration. The ECG will be measured with the subject in a resting position for at least 1 minute. No continuous ECG monitoring will be required. At a minimum the heart

rate, QRS, PR and QT intervals will be collected. QTc will be calculated using both the Fridericia and Bazett formulas.

On-site investigator's responsibilities

The immediate cardiac safety of the subject will be ensured by the on-site qualified physician. Any 12-lead ECG intervals, waveform abnormalities, and rhythm changes that are clinically significant in that they result in a change in subject management will be considered an AE. In the case of an SAE, once SAE notification is decided upon, investigators are required to follow the procedure described for SAE notification and document abnormal ECG findings (intervals and waveforms). Any interval data or abnormal waveform finding that resulted in an AE (i.e., change of patient management) must be followed to normalization or stabilization.

Each 12-lead ECG tracing must be signed and dated and stored in the subject's source documentation.

8.4.2.4 Clinical Laboratory Parameters for Screening and Safety

Clinical laboratory tests to be evaluated in this study include hematology, serum chemistry, and urinalysis. Clinical laboratory tests will include the following as defined in Table 2.

Table 2. Clinical Laboratory Parameters

Hematology	Hemoglobin (Hgb), hematocrit (HCT), platelets, neutrophils, basophils, lymphocytes, monocytes, red blood cells (RBC), white blood cells (WBC)
Serum chemistry	Aspartate aminotransferase (AST), alanine aminotransferase (ALT), alkaline phosphatase, total bilirubin, creatinine, chloride, hemoglobin A1c (screening only), potassium, sodium, total protein, albumin, carbon dioxide (CO ₂)/bicarbonate, blood urea nitrogen (BUN), glucose
Urinalysis	pH, specific gravity

All laboratory reports must be promptly reviewed for clinical significance by the investigator, and upon review, initialed and dated by the investigator.

Good clinical practice would suggest that a copy of the laboratory results also be provided to the subject's referring physician.

Any change in a laboratory value, which results in a change in subject management (additional controls or treatment required), will be reported as a clinically significant change. Clinically significant changes in laboratory parameters, which are not the result of laboratory error, are to be recorded as AEs.

Clinical Study Protocol Number: NAV3-30

Any clinically significant changes in laboratory values are to be followed up with repeated tests at appropriate intervals (as determined by the investigator) until the values return to baseline level or until the abnormality is explained by the investigator.

The expected amount of blood to be withdrawn is shown in Table 3.

Table 3 Approximate Amount of Blood Withdrawn

Time point of examination		Blood Volume
Screening: Laboratory examination	Chemistry 5 mLs Hematology 4 mLs	9 mL (~2 tsp)
Post Tilmanocept Injection and Imaging: Laboratory examination	Chemistry 5 mLs Hematology 4 mLs	9 mL (~2 tsp)
TOTAL:		18 mL (~4 tsp)

9 STATISTICAL METHODS

This is a prospective, open-label, multicenter, safety, comparative study of injected Tc 99m tilmanocept and unfiltered Tc 99m sulfur colloid in the detection of and assessment of localization (tessellation discrimination) to the liver in subjects with and without moderate to severe NASH by planar and SPECT/CT imaging. The statistical objective of the study is to determine the safety of Tc 99m tilmanocept and to compare Tc 99m tilmanocept localization (tessellation characteristics) to unfiltered Tc 99m sulfur colloid between subjects with and without NASH.

Exploratory contrasts with available elastography and Tc99m tilmanocept images may be completed.

A study center is defined as a treatment administration site or group of treatment administration sites under the control and supervision the same PI.

9.1 Randomization Methods

The study is not randomized.

9.2 Safety Variables

The primary variable for this study is whether a subject observes any noxious pharmacologic activity/adverse drug reaction (ADR) during their enrollment in the trial. This is a safety endpoint. The pharmacologic activity or ADR must be observed after the dose of Tc99m tilmanocept is administered.

NOTE: Adverse Drug Reaction

An ADR includes all noxious and unintended responses to a medicinal product related to any dose or dose regimen. The phrase "responses to a medicinal product" means that a casual relationship between a medicinal product and an AE is at least a reasonable possibility, i.e. the relationship cannot be ruled out.

9.3 Efficacy Variables

The efficacy variables for this study are as follows:

- Liver uptake of unfiltered Tc99m-labeled sulfur colloid and tilmanocept; and,
- Intrahepatic distribution (tessellation) of Tc99m-labeled sulfur colloid and tilmanocept

9.4 Sample Size Justification

The sample size of N=12 subjects is deemed sufficient to accomplish the Sponsor's objectives of determining the safety of IV tilmanocept and localization patterns of tilmanocept and sulfur colloid in NASH and asymptomatic subjects.

Tc 99m tilmanocept Clinical Study Protocol Number: NAV3-30

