 - Planar imaging of the liver/spleen followed by SPECT/CT of the liver/spleen and abdomen

Visit 3, Day 3:

Pre-Tc 99m Tilmanocept Administration:

- Before administration (Day 3)
 - Urine pregnancy test will be performed for subjects of childbearing potential
 - Assessment of adverse events

Confidential Page 10 of 71

	Concomitant medication review			
	o Vital Signs - within 15 minutes			
	administration	 		
	Tc 99m Tilmanocept Administration: Subjects will receive the open label 200 μg at the specified radiolabeled dose.			
	Post-Tc 99m Tilmanocept	Administration:		
	• 20 ± 5 Minutes Post-Administration:			
	o Assessment o	f adverse events		
	o ECG (comple	eted before vital signs)		
	 Vital Signs 			
		ng of the liver/spleen followed by f the liver/spleen and abdomen		
	• 75 ± 15 Minutes Pos	t-Administration:		
	o Assessment o	f adverse events		
	 Planar imaging of the liver/spleen followed by SPECT/CT of the liver/spleen and abdomen 			
	• 180 ± 15 Minutes Post-Administration:			
	 Assessment of adverse events 			
	 Planar imaging of the liver/spleen followed by SPECT/CT of the liver/spleen and abdomen 			
	After Completion of All Imaging:			
	o Blood draw testing	for hematology and chemistry		
	 Urine collecti 	on for urinalysis		
	Day 8 ± 3 :			
	Safety Follow-Up Telephor of Tc 99m Tilmanocept:	ne Call 5 ± 3 Days Post-Injection		
	Concomitant medica	tion review		
	Assessment of adverse events			
Planned study dates	Planned study dates Start of study recruitment / November 2018			
	End of Study/September 2018			
Planned number of study centers	Approximately 1-3 centers in the United States			
Number of subjects	Up to 12 evaluable subjects may be enrolled.			
.	J,			

Confidential Page 11 of 71

Primary Endpoint	Proportion of subjects experiencing a noxious pharmacologic activity/adverse drug reaction (ADR)	
Secondary Endpoints	Determine the three dimensional tessellation localization of Tc 99m tilmanocept by planar and SPECT/CT imaging in subjects with NASH and asymptomatic controls.	
	Determine the three dimensional tessellation localization of unfiltered Tc 99m sulfur colloid by planar and SPECT/CT imaging in subjects with NASH and asymptomatic controls.	
	Comparison of liver localization distribution tessellation pattern intensities between Tc 99m tilmanocept and unfiltered Tc 99m sulfur colloid	
Exploratory Endoints	*	

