	Concordance of intrahepatic localization tessellation discrimination of Tc 99m sulfur colloid (intrahepatic disease heterogeneity) by SPECT/CT imaging and elastography	
Data Analyses	The following analysis population will be defined for the study:	
	• Intent-to-Diagnose (ITD) Population - Subjects who are enrolled in the study, administered Tc 99m tilmanocept and unfiltered Tc 99m sulfur colloid, and are imaged will be included in the ITD analysis population.	
	• Safety Population – All patients who are enrolled and administered Tc 99m tilmanocept and unfiltered Tc 99m sulfur colloid in the study will be included in the safety population.	
	All safety data analyses will be conducted on the safety population. All efficacy data analyses will be conducted on the ITD population.	
	The number and percentage of subjects experiencing noxious pharmacologic activity or ADRs will be tabulated by subject type, Tc 99m tilmanocept dose group (if applicable), and overall.	

Confidential Page 12 of 71

Tc 99m tilmanocept Clinical Study Protocol Number: NAV3-30

> Per subject localization rates and percentage will be calculated by time point, by subject type, Tc 99m tilmanocept dose group (if applicable), and overall.

> Localization intensities (tessellation) will be summarized by descriptive statistics (mean, median, standard deviation, minimum, maximum and range) at each time point. All results will be compared to statistics computed on the control group at each time point.

Confidential Page 13 of 71

Clinical Study Protocol Number: NAV3-30

LIST OF ABBREVIATIONS AND DEFINITIONS OF TERMS

ADR adverse drug reaction

AE adverse event

ALT alanine aminotransferase (SGPT)

AST aspartate aminotransferase (SGOT)

[figure not shown]
BMI body mass index

BUN blood urea nitrogen

CCL2 CC-chemokine ligand 2

CCR2 CC-chemokine receptor 2

CD206 Mannose-binding receptor (Ca2+-binding lectin)

CO₂ carbon dioxide

CRA clinical research associate

CRF case report form

CRO contract research organization

CSF1 Macrophage colony-stimulating factor 1

CSF1R CSF1 receptor

CT X-ray computed tomography

CX3CR1 CX3C-chemokine receptor 1

CXCL CXC-chemokine ligand

CXCR CXC-chemokine receptor

Clinical Study Protocol Number: NAV3-30

Cy3 cyanine dyes fluoresce orange (~550 nm excitation, ~570 nm

emission)

$$\begin{array}{c|c} & 1 & 3 \\ & & 1 \\ \hline & 1 \\ & & R \\ & & Cy3 \end{array}$$

DAMPs Damage-associated molecular patterns

DICOM Digital Imaging Communications in Medicine

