2 STUDY OBJECTIVES

2.1 Primary Objective(s)

• Determine the safety and tolerability of Tc 99m tilmanocept in subjects with NASH.

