5.2 Investigational Product Dosage and Administration

[figure not shown]
On Day 0, subjects will receive an on label 8.0 mCi dose of unfiltered Tc 99m sulfur colloid via IV administration. On Day 3, subjects will receive 200 μg tilmanocept via IV administration at the specified radiolabeled dose of Tc 99m. A single syringe will be used for each product and injected as a slow push into the IV. At the completion of each injection, a 10 cc sterile normal saline flush will be administered. The preferred site of IV placement will be the left or right antecubital vein. The final administered tilmanocept dose will be \pm 20% of the mass dose and radiolabel mCi dose assignment.

The first two enrolled subjects will be NASH subjects who will receive an 8.0 mCi radiolabel dose of Tc 99m tilmanocept. A review meeting will be held following completion of the first two subjects to evaluate tilmanocept safety and dose performance.

At the review (as diagrammed below):

- 1. If it is determined that a lower radiolabel dose of tilmanocept may produce images of better quality, three additional NASH subjects and three HCs will be injected and imaged with 200 µg of 2.5 mCi Tc 99m tilmanocept. After these six subjects have completed the trial, no additional subjects will be enrolled.
- 2. If the review shows no safety signals and acceptable quality of imaging, one additional NASH subject as well as three HCs will be injected and imaged with 200 μg of 8.0 mCi Tc 99m tilmanocept. Once a total of three NASH subjects and three HCs have completed the trial, a second review meeting will be held to compare results from NASH subjects to those of the HCs. If it is determined at the second review meeting that a lower radiolabel dose of tilmanocept may produce additional clinically meaningful results, 3 NASH subjects and 3 HCs will be dosed with 200 μg of 2.5 mCi Tc 99m tilmanocept. If it is determined that additional doses will not provide clinically meaningful results, the trial will be concluded.

Confidential Page 39 of 71

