8 PROCEDURES AND VARIABLES

8.1 Population Characteristics

8.1.1 Demographic and Other Baseline Characteristics

Up to six (6) female or male subjects with biopsy-confirmed moderate to severe NASH will be enrolled. Up to six (6) female or male subjects without evidence of any liver or inflammatory diseases will be enrolled. There are no minimum or maximum numbers for gender in the groups.

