9.5.4 Analysis of Safety Variables

The number and percentage of subjects with any noxious pharmacologic activity or ADRs will be tabulated by dose group and overall.

All AEs will be observed for each subject from the time of signing of informed consent until exit from the study. A treatment emergent AE is defined as an AE whose start date is on or after the procedure date. If the procedure date and/or the AE start date are missing, the AE will be considered treatment emergent.

Prior to analysis, all AEs will be coded using the MedDRA coding dictionary. Based on these coded terms, treatment emergent AEs will be summarized by dose group and overall as follows:

- by system organ class and preferred terms
- by system organ class and preferred terms and relation to study drug
- by system organ class and preferred terms and severity

Observed and change from baseline vital sign parameters, ECG parameters and hematology, clinical chemistry and urinalysis parameters will be summarized using descriptive statistics (mean, median, standard deviation, minimum, maximum and range) at each time point by dose group and overall.

Other safety analyses will be described in the SAP for the study.

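### Section 9.4 calls N=12 sufficient to determine safety, but Section 5.2 can end at 6, 8 or 12 subjects (3, 5 or 6 with NASH), no precision is given at any size, and Section 9.5.4 has no NASH row for the primary endpoint

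*Combined protocol and SAP*

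**What the plan says.** The whole sample size justification in Section 9.4 is one sentence: "The sample size of N=12 subjects is deemed sufficient to accomplish the" sponsor's aims on the safety of IV tilmanocept and on localization patterns. It gives no assumed ADR rate, confidence level, precision or detectable rate, and none appears elsewhere for the safety endpoint.

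Other parts of the protocol treat 12 as a cap. The synopsis says "Up to 12 evaluable subjects may be enrolled". Section 8.1.1 says "Up to six (6) female or male subjects with biopsy-confirmed moderate to severe NASH will be enrolled" and sets the same ceiling for controls.

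Section 5.2 (repeated in the synopsis) starts with two NASH subjects and then branches at a review. On the first outcome, three more NASH subjects and three controls are added, and "After these six subjects have completed the trial, no additional subjects will be enrolled". On the second, one more NASH subject and three controls are added and a second review follows. That review either adds three NASH subjects and three controls at the lower radiolabel dose or stops: "If it is determined that additional doses will not provide clinically meaningful results, the trial will be concluded".

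The primary objective (Section 2.1) is "Determine the safety and tolerability of Tc 99m tilmanocept in subjects with NASH", and the primary endpoint is the proportion of subjects with an ADR. The synopsis says ADRs "will be tabulated by subject type, Tc 99m tilmanocept dose group (if applicable), and overall". Section 9.5.4 says only that "noxious pharmacologic activity or ADRs will be tabulated by dose group and overall". Both give a number and a percentage, with no interval.

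**The concern.** There are three linked problems.

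First, Section 9.4 rests its claim on a size that the design delivers on only one of its three stated paths, and it is the most favourable of the three.

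Second, the claim has nothing behind it at any size, 12 included. Without a precision statement, a reader cannot tell what sufficient means.

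Third, the statistical section gives the primary endpoint no row for the population named in the primary objective. Controls also receive tilmanocept, so the overall proportion is informative. But it always mixes NASH subjects with controls.

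Zero ADRs is a plausible result at these sizes. Section 1.4.4 reports no adverse events attributed to tilmanocept so far in the ongoing IV study in rheumatoid arthritis. A bare 0% from a sample described as sufficient to determine safety would claim more than the data can show, most of all for the NASH subjects.

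**Working it through.** **Step 1: planned completers on each path (Section 5.2).**

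- First review, outcome 1: 2 NASH + 3 NASH + 3 controls = 8, of whom 5 have NASH.
- Outcome 2, concluded at the second review: 2 NASH + 1 NASH + 3 controls = 6, of whom 3 have NASH.
- Outcome 2 with the lower dose added: 6 + 3 NASH + 3 controls = 12, of whom 6 have NASH.

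The stated N=12 is therefore reproduced as a head count on the third path only. It cannot be reproduced by a sample size formula, because the protocol gives no inputs for one.

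**Step 2: what the dose-group rows in Section 9.5.4 would contain.**

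- 8-subject path: 2 NASH at 8.0 mCi; 3 NASH + 3 controls at 2.5 mCi.
- 6-subject path: 3 NASH + 3 controls at 8.0 mCi.
- 12-subject path: 3 NASH + 3 controls at each dose.

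The only row without controls is the two-subject 8.0 mCi group on the 8-subject path, and it leaves out the other three NASH subjects. No row on any path shows all NASH subjects.

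**Step 3: precision if no ADR is seen.** The two-sided 95% Clopper-Pearson upper bound for 0/n is 1 − 0.025^(1/n). For n = 3 this is 1 − 0.025^(1/3) = 0.708; for n = 12 it is 1 − 0.025^(1/12) = 0.265. The one-sided 95% bound is 1 − 0.05^(1/n).

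**Step 4: chance of seeing no ADR at a true rate p,** which is (1 − p)^n. The rates of 10% and 20% are illustrative assumptions; the protocol gives none. For n = 3 and p = 20%, 0.8^3 = 0.512.

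| n | Arises as | Upper bound for 0/n, two-sided 95% | Upper bound for 0/n, one-sided 95% | P(no ADR), p = 10% | P(no ADR), p = 20% |
|---|---|---|---|---|---|
| 3 | NASH, 6-subject path | 70.8% | 63.2% | 72.9% | 51.2% |
| 5 | NASH, 8-subject path | 52.2% | 45.1% | 59.0% | 32.8% |
| 6 | NASH, 12-subject path; all, 6-subject path | 45.9% | 39.3% | 53.1% | 26.2% |
| 8 | All, 8-subject path | 36.9% | 31.2% | 43.0% | 16.8% |
| 12 | All, 12-subject path | 26.5% | 22.1% | 28.2% | 6.9% |

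With three NASH subjects, a true ADR rate of 20% would go unseen about half the time.

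**The case against.** This is a small descriptive phase 1 feasibility study. It sets no ADR threshold, and none of the review decisions in Section 5.2 depends on an ADR proportion or its bound. Such a study needs no power calculation. No figure in the protocol is miscalculated: 12 follows from the longest path, and the synopsis, Section 8.1.1 and Section 5.2 let a reader recover every size. The synopsis already plans ADRs by subject type, and the SAP may add intervals. Anyone with a count and a denominator can compute an exact interval. The bounds also depend on convention: at one-sided 95% they fall to 22% to 39% overall and 39% to 63% in NASH.

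Much of this is fair. The lack of a power calculation is not an error, and the NASH proportion is not missing from the protocol as a whole. What remains is narrower. Section 9.4 makes a positive claim of sufficiency, ties it to one of three planned sizes, and supports it with nothing. Section 9.5.4 and the synopsis describe the analysis of the primary endpoint differently, and the statistical section is the one that drops the population in the objective. Section 9.5.4 leaves only other safety analyses to the SAP; it specifies the ADR tabulation itself. No SAP text was available for this check, so an interval or a subject-type table there cannot be ruled out. The mismatch within the protocol would still stand. The one-sided convention changes the numbers but not the message.

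**Conclusion.** The concern holds. The planned size is 6, 8 or 12 completers, with 3, 5 or 6 NASH subjects, and the statement that 12 is sufficient is unsupported at every one of these sizes. With zero ADRs, the two-sided 95% upper bound is 46%, 37% or 26% for all exposed subjects (n = 6, 8, 12) and 71%, 52% or 46% for NASH subjects (n = 3, 5, 6). As Section 9.5.4 stands, no tabulated row answers the primary objective.

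The bounds assume zero events, a 95% confidence level and completer counts taken from the stated branches. Two limits apply to those counts:

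- Under Sections 4.4 and 9.5.1, a subject who received both agents but was not imaged is replaced yet stays in the safety population, so its n can be larger.
- Section 5.2 states no path, and so no N, if the first review finds a safety signal. Sections 10.6 and 10.6.1 allow the sponsor to terminate for safety or medical reasons, so fewer subjects are also possible.

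This should be corrected: it affects how the primary result can be read, but not how the trial is run.

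**What to change.** - **Section 9.4:** give 12 as the maximum and list planned completers by decision path: 6, 8 or 12, with 3, 5 or 6 NASH subjects. Add the two limits on these counts (replacement of subjects who were dosed but not imaged, and no stated N after a safety signal at the first review). Replace the sufficiency claim with the zero-event upper bounds, overall and for NASH subjects, and state the confidence level used.
- **Section 9.5.4:** bring it into line with the synopsis by tabulating ADRs by subject type as well as by dose group and overall. Report an exact (Clopper-Pearson) 95% interval for the ADR proportion in NASH subjects and in all exposed subjects. Make sure the SAP says the same.

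The cost is a few lines of text, one table dimension that the synopsis already promises, and one interval per proportion. No subjects are added, and no dose or clinical rule changes. The only downside is that the stated precision will look less favourable.
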